6.1 Dose Delays/Dose Modifications

Guidelines for delaying, restarting, or discontinuing therapy for various toxicities is included in sections 17.1 and 17.2. Dose modifications are not permitted for this protocol, except if Day 1 weight change by >10% necessitates a change in the dosing of cabiralizumab. If therapy is delayed, then next infusion date will be considered day 1 of the subsequent cycle.

In addition to sections 17.1 and 17.2, please see below for dose delays related to hematologic toxicity:

- For Grade 1-2 (neutrophils <LLN to 1,000/ μ L, hemoglobin <LLN to 8 g/dL, platelets <LLN to 50,000/ μ L)
 - Rule out alternative causes
 - Continue cabiralizumab and nivolumab therapy
 - Monitor CBC per schedule of events
 - If worsens, treat as grade 3-4 toxicity
- For Grade 3-4 (neutrophils < 1,000/ μ L, hemoglobin < 8 g/dL, platelets < 50,000/ μ L)
 - Rule out alternative causes
 - Delay cabiralizumab and nivolumab therapy. If the AE requiring dose delay was due to one of the study drugs, the non-offending drug may be continued, taking into account the safety and clinical benefit to the patient.
 - Treat autoimmune cytopenias per standard institutional guidelines (examples below):
 - Immune thrombocytopenia may be treated with steroids, immune globulin, or rituximab
 - Immune mediated hemolytic anemia may be treated with steroids, immune globulin, or rituximab
 - Immune mediated neutropenia may be treated with steroids, colony stimulating factors, or immune globulin
 - If improves to < grade 3:

- May resume cabiralizumab and nivolumab therapy per protocol
- If does not improve or worsens:
 - Discontinue therapy. If the AE requiring discontinuation was due to one of the study drugs, the non-offending drug may be continued, if there is timely resolution of AE and clinical benefit is shown by patient.
 - Continue to treat immune mediated cytopenias per standard algorithms
 - Continue follow up until resolution
- Grade 3 drug-related thrombocytopenia associated with grade ≥ 2 bleeding requires discontinuation regardless of duration of thrombocytopenia.

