AST or ALT > 12 to ≤ 20 xULN and Total bilirubin ≤ 2 xULN or Isolated total bilirubin > 2 to ≤ 3 xULN	
 – Delay cabiralizumab and nivolumab therapy per protocol^a – Increase frequency of monitoring of (including but not limited to) AST, ALT, bilirubin, alkaline phosphatase and INR (every 48-72 hours or more frequently, as clinically indicated) – If there is a 2-fold ALT increase compared to the previous measurement, start steroids immediately – Consider steroid treatment on any total bilirubin increase of over 2.0x ULN – If there is a concurrent increase of alkaline phosphatase along with ALT, start steroids immediately – Monitor for other clinical symptoms (fatigue, nausea, vomiting, abdominal pain, fever, rash, and/or eosinophilia) 	
If AST/ALT return to ≤ 12 xULN within ≤ 7 days:
 
 – Resume routine monitoring – Resume cabiralizumab and nivolumab therapy at same dose level per protocol 
If elevations persist and remain at the same level > 7 days but < 28 days:
 
 – Start steroids immediately and discontinue further dosing – Continue monitoring and consider dosing the subject with nivolumab therapy at the same dose level 
Consider tapering steroids over at least 1 month
 
If elevations persist at the same level > 28 days or worsen:
 
 – Discontinue cabiralizumab and nivolumab therapy per protocol – 0.5-1 mg/kg/day methylprednisolone or oral equivalent and when LFT returns to Grade 1 or baseline, taper steroids over at least 1 month – Consider prophylactic antibiotics for opportunistic infections – Discuss with Sponsor Investigator

Hepatic Adverse Event Management without Liver Metastasis		
Rule out noninflammatory causes. If a noninflammatory cause is identified, treat accordingly and continue nivolumab therapy. Consider imaging for obstruction.		
Grade of Liver Test Elevation	Management	Follow-Up

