17.1.3 Hepatic toxicity management with liver metastasis

Hepatic Adverse Event Management with Liver Metastasis		
Rule out noninflammatory causes. If a noninflammatory cause is identified, treat accordingly and continue nivolumab therapy. Consider imaging for obstruction.		
Grade of Liver Test Elevation	Management	Follow-Up
AST or ALT >3.0x ULN and Total bilirubin >2x ULN or INR > 1.5	
 - Discontinue cabiralizumab and nivolumab therapy per protocol - Start steroids 	
 - Continue LFT monitoring per protocol until resolution. - Continue monitoring for and other associated clinical signs or symptoms - Contact the Sponsor Investigator - Evaluate for non drug related causes of the laboratory abnormalities (e.g. obstruction, viral infection, Gilbert’s disease, etc) - Under selected circumstances (e.g alternative etiology is identified), patient may receive additional therapy only after consultation and agreement between the Sponsor/MM and the investigator if receiving additional treatment with cabiralizumab and nivolumab is in the best interest of the patient (e.g if the subject has demonstrated a response to therapy)
AST or ALT > 5 to ≤ 12 xULN and Total bilirubin ≤ 2 xULN	
 - Continue cabiralizumab and nivolumab therapy if there are no clinical signs of significant muscle or hepatic damage - Increase frequency of monitoring of AST, ALT, bilirubin, alkaline phosphatase and INR (every 48-72 hours or more frequently, as clinically indicated) - Monitor for other clinical symptoms (fatigue, nausea, vomiting, abdominal pain, fever, rash, and/or eosinophilia) 	
 - Contact the Sponsor Investigator if there are clinical signs of muscle or hepatic injury or other clinical symptoms - Contact the Sponsor Investigator if there is a concurrent increase of bilirubin, AST, ALT, or alkaline phosphatase - Notify the Sponsor Investigator if there is an AST or ALT increase > 5 xULN - Frequency of retesting can decrease to once a week or less if abnormalities stabilize or the trial drug has been discontinued and the subject is asymptomatic - Consider gastroenterology or hepatology referral

Hepatic Adverse Event Management with Liver Metastasis		
Rule out noninflammatory causes. If a noninflammatory cause is identified, treat accordingly and continue nivolumab therapy. Consider imaging for obstruction.		

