Grade of Liver Test Elevation	Management	Follow-Up
AST or ALT > 12 to ≤ 20 xULN and Total bilirubin ≤ 2 xULN or Isolated total bilirubin > 3.0 to ≤ 5 xULN	
 - Delay cabiralizumab and nivolumab therapy per protocol^a - Increase frequency of monitoring of (including but not limited to) AST, ALT, bilirubin, alkaline phosphatase and INR (every 48-72 hours or more frequently, as clinically indicated) - If there is a 2-fold ALT increase compared to the previous measurement, start steroids immediately - Consider steroid treatment on any total bilirubin increase of over 2.0x ULN - If there is a concurrent increase of alkaline phosphatase along with ALT, start steroids immediately - Monitor for other clinical symptoms (fatigue, nausea, vomiting, abdominal pain, fever, rash, and/or eosinophilia) 	
If AST/ALT return to ≤ 12 xULN within ≤ 7 days:
 
 - Resume routine monitoring, resume cabiralizumab and nivolumab therapy at same dose level per protocol 
If elevations persist and remain at the same level > 7 days but < 28 days:
 
 - Start steroids immediately and discontinue further dosing - Continue monitoring and consider dosing the subject with nivolumab therapy at the same dose level - Consider tapering steroids over at least 1 month 
If elevations persist at the same level >28 days or worsen:
 
 - Discontinue cabiralizumab and nivolumab therapy per protocol - 0.5–1 mg/kg/day methylprednisolone or oral equivalent and when LFT returns to Grade 1 or baseline, taper steroids over at least 1 month - Consider prophylactic antibiotics for opportunistic infections - Discuss with Sponsor Investigator

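### The hepatic delay rows can be entered on bilirubin alone, but their only resume test is on AST/ALT, so the written restart rule does not work for that trigger

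*Combined protocol and SAP*

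**What the plan says.** Section 6.1 names the place where restart rules are kept: "Guidelines for delaying, restarting, or discontinuing therapy for various toxicities is included in sections 17.1 and 17.2". Section 6.1 itself adds rules for hematologic toxicity only.

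The delay row in each hepatic table has two alternative triggers. The first is AST/ALT above 12 and up to 20 xULN with total bilirubin no higher than 2 xULN. The second is bilirubin alone: "Isolated total bilirubin > 2 to ≤ 3 xULN" in 17.1.2 and "Isolated total bilirubin > 3.0 to ≤ 5 xULN" in 17.1.3. Either trigger delays both drugs.

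Three follow-up branches then serve both triggers, and both tables set the same three conditions:

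- "If AST/ALT return to ≤ 12 xULN within ≤ 7 days": resume both drugs at the same dose level.
- "If elevations persist and remain at the same level > 7 days but < 28 days": start steroids, stop further dosing, and consider nivolumab.
- "If elevations persist at the same level > 28 days or worsen": discontinue both drugs.

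Two further rows bound the delay row. Combined abnormality leads to discontinuation: "AST or ALT >3.0x ULN and Total bilirubin >2x ULN or INR > 1.5" (same limits in both tables). So does AST/ALT above 20 xULN, or bilirubin above 3 xULN (17.1.2) or above 5 xULN (17.1.3).

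**The concern.** The resume rule tests a different analyte from the one that caused the delay. A patient can be held for bilirubin alone, yet the only written way back to both drugs is an AST/ALT value.

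The choice of analyte matters with this regimen. Section 1.6.3 treats enzyme rises under cabiralizumab as a pharmacodynamic effect of Kupffer cell depletion, and lists bilirubin, with INR and ALT/AST, among the measures that should rule out real hepatic injury. For the bilirubin trigger, the written restart test relies on the enzymes and leaves bilirubin out. Each site in a multicenter trial must then infer the bilirubin level at which to restart, and sites could infer different levels for similar patients.

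**Working it through.** No sample size, power or error rate is involved. The check sets the rows against each other and follows a bilirubin-only patient through them.

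**Step 1: AST/ALT ceiling for this patient.** On entry, bilirubin is above 2 xULN (17.1.2) or above 3 xULN (17.1.3), so above 2 xULN in both. If AST or ALT were also above 3 xULN, the combined discontinue row would apply. A patient in the delay row on bilirubin alone therefore has AST/ALT ≤ 3 xULN. The resume limit is 12 xULN. Since 3 < 12, the patient did not exceed the resume limit at the start of the delay.

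**Step 2: the three branches, with bilirubin falling.**

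| Branch | Tests | Result for this patient |
|---|---|---|
| Resume both drugs | AST/ALT ≤ 12 xULN within ≤ 7 days | Met at once, whatever the bilirubin; or, if return requires an earlier rise above 12 xULN, never met |
| Stop, consider nivolumab | Elevation unchanged, > 7 to < 28 days | Not applicable: bilirubin is improving |
| Discontinue both | Elevation unchanged > 28 days, or worse | Not applicable: bilirubin is improving |

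None of the 3 branches states a bilirubin value for restart. The last two speak of elevations in general, so bilirubin that persists or worsens is covered.

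**Step 3: other places.** Section 6.1 restarts on hematologic recovery ("If improves to < grade 3"). Section 6.3 asks for Medical Monitor consultation after a delay of more than 6 weeks and gives no bilirubin threshold. Section 17.2 covers CK and LDH. Table footnote a concerns continuing the non-offending drug during a delay. The consultation route in the combined discontinue row is discretionary, has no laboratory restart test and does not address isolated bilirubin. None of these supplies the missing value.

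**Step 4: would a bilirubin-only exit do?** No; it would collide with other rows.

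- In 17.1.3, bilirubin of 2.5 xULN with AST at 4 xULN would meet an exit at ≤ 3 xULN and also the discontinue row (AST > 3 and bilirubin > 2 xULN).
- In 17.1.2, bilirubin ≤ 2 xULN with AST at 15 xULN would meet an exit at ≤ 2 xULN and also the delay trigger (AST > 12 to ≤ 20 xULN).

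The test has to be joint. It also has to deal with a value still improving after day 7. Step 2 shows that no branch fits such a patient, and the same is true of AST/ALT that is falling but still above 12 xULN on day 7.

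**Step 5: are the data available?** The row already requires bilirubin every 48 to 72 hours. Seven days is 7 × 24 = 168 hours; 168/72 = 2.3 and 168/48 = 3.5, so 2 to 3 results fall inside the window.

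**The case against.** The strongest answer is that the rows follow current laboratory values. While bilirubin is in the delay range, the row says delay. Once it falls below that range with AST/ALT ≤ 3 xULN and INR ≤ 1.5, no row calls for a hold and ordinary 14-day dosing applies. On that view the restart value can be inferred, and an early restart would contradict the row itself. Section 17.1 also describes the tables as guidance that may be supplemented by discussion with the Sponsor Investigator. The table headers ask sites to look for noninflammatory causes and to continue nivolumab if one is found.

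Most of this stands, and it keeps the risk small. It does not make the written rule correct: the row does state a resume condition, and applied to its own second trigger that condition gives no usable answer.

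Two stronger readings should be resisted. A reader might infer that patients would be redosed with raised bilirubin; the delay instruction in the same row makes that unlikely. A reader might also infer that the hepatic tables are the only delay rules without a working restart test. The documents do not support that. In 17.1.5, Grade 1 pneumonitis allows a delay with no restart test, and in 17.1.6 the suspected adrenal crisis row shows none, although that table may have been broken in extraction.

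**Conclusion.** The point holds as a drafting defect with a small safety consequence. In one row of each of two tables, the only resume rule tests AST/ALT ≤ 12 xULN, a limit that a patient delayed on bilirubin alone did not exceed. The gap is confined to patients whose bilirubin is recovering.

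Few of the 33 subjects are likely to be affected. That is a judgement, since the documents give no expected frequency. No response rate, stopping boundary, sample size, error rate or power figure changes.

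The conclusion rests on reading the combined discontinue row as taking precedence whenever AST/ALT exceeds 3 xULN with bilirubin above 2 xULN, as the tables state.

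**What to change.** In both tables, replace the resume condition with a joint test and keep the 7-day window:

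*If, within ≤ 7 days, AST/ALT are ≤ 12 xULN and total bilirubin is ≤ 2 xULN (17.1.2) or ≤ 3 xULN (17.1.3), and no discontinue criterion is met (including AST/ALT > 3 xULN with bilirubin > 2 xULN, or INR > 1.5), resume cabiralizumab and nivolumab at the same dose level.*

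Add that values improving after day 7 but not yet meeting this test stay on delay, and that dosing may resume when they meet it, within the existing 28-day limit.

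The bilirubin values are the lower ends of each row's own entry range. The sponsor should confirm the 17.1.3 value clinically, because the same row advises considering steroids once bilirubin rises above 2 xULN.

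A return-to-baseline alternative should not be added. Section 3.1 admits subjects with Gilbert's syndrome with total bilirubin below 3 mg/dL. At an assumed ULN of 1.0 to 1.2 mg/dL (not given in the documents), that ceiling is 3/1.0 = 3.0 to 3/1.2 = 2.5 xULN, which is above the 2 xULN entry trigger in 17.1.2.

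The cost is one line in each of two tables, in an amendment. No extra tests are needed.

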17.1.2 Hepatic toxicity management without liver metastasis

Hepatic Adverse Event Management without Liver Metastasis		
Rule out noninflammatory causes. If a noninflammatory cause is identified, treat accordingly and continue nivolumab therapy. Consider imaging for obstruction.		
Grade of Liver Test Elevation	Management	Follow-Up
AST or ALT >3.0x ULN and Total bilirubin >2x ULN or INR > 1.5	
 – Discontinue cabiralizumab and nivolumab per protocol – Start steroids 	
 – Continue LFT monitoring per protocol until resolution. – Continue monitoring for and other associated clinical signs or symptoms – Contact the Sponsor Investigator – Evaluate for non drug related causes of the laboratory abnormalities (e.g. obstruction, viral infection, Gilbert’s disease, etc) – Under selected circumstances (e.g alternative etiology is identified), patient may receive additional therapy only after consultation and agreement between the Sponsor/MM and the investigator if receiving additional treatment with cabiralizumab and nivolumab is in the best interest of the patient (e.g if the subject has demonstrated a response to therapy)
AST or ALT > 5 to ≤ 12 xULN and Total bilirubin ≤ 2 xULN	
 – Continue cabiralizumab and nivolumab therapy if there are no clinical signs of significant muscle or hepatic damage – Increase frequency of monitoring of AST, ALT, bilirubin, alkaline phosphatase and INR (every 48-72 hours or more frequently, as clinically indicated) – Monitor for other clinical symptoms (fatigue, nausea, vomiting, abdominal pain, fever, rash, and/or eosinophilia) 	
 – Contact the Sponsor Investigator if there are clinical signs of muscle or hepatic injury or other clinical symptoms – Contact the Sponsor Investigator if there is a concurrent increase of bilirubin, AST, ALT, or alkaline phosphatase – Notify the Sponsor Investigator if there is an AST or ALT increase > 5 xULN – Frequency of retesting can decrease to once a week or less if abnormalities stabilize or the trial drug has been discontinued and the subject is asymptomatic – Consider gastroenterology or hepatology referral

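### In both hepatic toxicity tables, row 2's continue rule or row 3's resume rule can apply while row 1's discontinuation rule is also met, and no row priority is written

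*Combined protocol and SAP*

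**What the plan says.** Rows are counted from the top of each table; the points below are the same in 17.1.2 and 17.1.3.

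- **Row 1.** The entry condition is "AST or ALT >3.0x ULN and Total bilirubin >2x ULN or INR > 1.5". Both drugs are discontinued and steroids are started. In selected circumstances, the "patient may receive additional therapy only after consultation and agreement between the Sponsor/MM and the investigator". Its monitoring line is "Continue LFT monitoring per protocol until resolution".
- **Row 2.** The entry condition is "AST or ALT > 5 to ≤ 12 xULN and Total bilirubin ≤ 2 xULN". The dosing instruction is "Continue cabiralizumab and nivolumab therapy if there are no clinical signs of significant muscle or hepatic damage". The sponsor-investigator is to be notified above 5x ULN.
- **Row 3.** The AST/ALT limb is >12x to ≤20x ULN with bilirubin ≤2x ULN. Both drugs are delayed. The resume condition is "If AST/ALT return to ≤ 12 xULN within ≤ 7 days", and the action is "Resume cabiralizumab and nivolumab therapy at same dose level per protocol" in 17.1.2 and "resume cabiralizumab and nivolumab therapy at same dose level per protocol" in 17.1.3.
- **INR.** Rows 2 and 3 order INR testing every 48-72 hours. Neither uses INR in its entry condition, its continue rule or its resume rule.

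Section 6.3 sends decisions on stopping for hepatic toxicity to these tables. Section 17.1 describes them as guidance to the site investigator.

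**The concern.** The bilirubin limit in rows 2 and 3 keeps a patient who qualifies for row 1 through bilirubin from also entering row 2 or row 3's AST/ALT limb. Nothing similar was done for row 1's other trigger, INR. Row 3's resume rule drops the bilirubin limit as well. One set of laboratory values can therefore call for two different dosing instructions.

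Patient safety is at stake. Section 1.6.3 accepts high enzyme values because they are attributed to the drug's mechanism, and names bilirubin, INR and ALT/AST as the extra checks for hepatic injury. Where INR, or bilirubin at the resume step, is abnormal, rows 2 and 3 as written permit dosing that row 1 allows only by agreement.

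**Working it through.** No figure in the plan needs reproducing; the check is one of logic.

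**Conditions.** Let A be AST or ALT (xULN), B total bilirubin (xULN) and I the INR.

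- Row 1, reading (i): A > 3 and (B > 2 or I > 1.5).
- Row 1, reading (ii): (A > 3 and B > 2) or I > 1.5. The text has no brackets, so both readings are tested.
- Row 2: 5 < A ≤ 12 and B ≤ 2.
- Row 3, AST/ALT limb: 12 < A ≤ 20 and B ≤ 2.
- Row 3, resume: A ≤ 12 within 7 days.

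**Entry overlap.** In row 2 and row 3's AST/ALT limb, A > 5, so A > 3 holds. B ≤ 2 closes the bilirubin route to row 1. That leaves I > 1.5, which is enough under either reading. Every combination in these rows with INR >1.5 therefore also meets row 1.

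An enumeration over A = 2, 4, 8, 12, 13, 20, 21; B = 1, 2, 2.5, 3, 4, 5, 6; and I = 1.0, 1.5, 1.6, 2.0 confirms this. Row 2 contains 2 × 2 × 4 = 16 combinations, of which 2 × 2 × 2 = 8 also meet row 1. Row 3's limb gives the same 16 and 8. Both tables and both readings agree. With INR ≤1.5 added, each row keeps 8 combinations and the overlap is 0. These counts show logic, not patient frequency.

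**Worked cases, as (A, B, I):**

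| Case | Rows met | Instructions |
|---|---|---|
| (8, 1, 1.6) | 1 and 2 | Discontinue both and start steroids; or continue both if no clinical signs |
| (16, 1, 1.0), then (10, 1, 1.6) by day 7 | Row 3 at entry; then row 3 resume and row 1 | Resume both at the same dose; or discontinue both |
| (16, 1, 1.0), then (10, 2.5, 1.0) by day 7 | Row 3 at entry; then row 3 resume and row 1 | Resume both at the same dose; or discontinue both |
| (16, 1, 1.0), then (10, 1, 1.0) by day 7 | Row 3 at entry; then row 3 resume only | No conflict with row 1 |
| (1, 1, 1.6) | None under (i); row 1 under (ii) | Depends on the missing brackets |

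**Does other text settle it?** Neither table, nor 6.3, nor the introduction to 17.1 gives a row priority. The potential drug-induced liver injury definition in 11.1.6 governs reporting, not dosing. It needs bilirubin >2x ULN and does not mention INR, so the INR cases do not reach it.

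**What a repair must cover.** An INR limit on entry alone leaves both day-7 conflicts. Adding INR to the resume condition closes the (10, 1, 1.6) case but not (10, 2.5, 1.0), because bilirubin is still unchecked there. Row 3 also has a branch for elevations lasting more than 7 and less than 28 days, which lets the site consider nivolumab; it carries no bilirubin or INR limit. A general priority for row 1 covers all of these.

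**The case against.** The strongest reply is that row 1 is itself the action for a raised INR, and that the INR tests ordered in rows 2 and 3 are there to detect it. Row 1's re-treatment wording is exclusive, so a patient already discontinued under it should not come back through row 3. A careful site would probably read the tables this way. The reply is weaker for (8, 1, 1.6), where both rows apply at once, and for a patient who enters row 3 with normal INR and worsens by day 7 on a value the resume rule does not check.

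Other safeguards stand. The tables are guidance. The sponsor-investigator is notified above 5x ULN, where all these conflicts arise. Section 6.3 discontinues a patient whose laboratory abnormality, in the investigator's opinion, poses substantial clinical risk. However, notification is weaker than agreement, and the 6.3 stop is discretionary.

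Some stronger readings are tempting but unsupported:

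- A reader might infer that row 1 is a temporary hold until the sponsor agrees. It is a discontinuation, with re-treatment possible in selected circumstances.
- A reader might infer that rows 1 and 3 agree on the day of the event because both withhold drug. Row 1 requires steroids; row 3 requires them at entry only for a 2-fold ALT rise or a concurrent rise in alkaline phosphatase. Row 3's footnote also lets a non-offending drug continue.
- A reader might infer that INR monitoring is unplanned, since the calendar's liver panel omits INR. Section 1.6.3 commits to it for elevated transaminases, and rows 2 and 3 order it.

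**Conclusion.** The inconsistency is real and appears in both tables under either reading of row 1. It affects patients with AST/ALT >5x to ≤20x ULN, bilirubin ≤2x ULN and INR >1.5, and patients who meet row 3's resume rule while row 1 is met through INR or bilirubin. For them the text gives conflicting dosing instructions and no rule for choosing between them.

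A reader might infer that patients will in fact be dosed against row 1, or that power, type I error or the interim rules are affected. The documents support neither. They give no frequency for these laboratory combinations, the safeguards make row 1 the likely choice at a cautious site, and no statistical figure changes. The point should be corrected as a safety clarification. The conclusion rests only on the table wording and the absence of a stated priority.

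**What to change.** In both 17.1.2 and 17.1.3:

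1. Add above the table: *If row 1 is met at any time, row 1 governs dosing, re-treatment and the start of steroids; the closer monitoring and escalation steps of the row matching the AST/ALT level still apply.* This is the core change. Its second half matters because row 1's own monitoring line sets no shorter interval, whereas rows 2 and 3 ask for tests every 48-72 hours and row 4 every 1 to 2 days.
2. Write row 1 as *AST or ALT >3x ULN and (total bilirubin >2x ULN or INR >1.5)*, if that is the intended reading.
3. For clarity, add *and INR ≤1.5* to row 2 and to row 3's AST/ALT limb, and make row 3's resume condition *AST/ALT ≤12x ULN within ≤7 days and row 1 not met*.

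The cost is wording in two appendix tables at the next amendment. The downside is that some patients whom rows 2 or 3 would keep on, or return to, treatment are discontinued unless re-treatment is agreed, as row 1 already requires. A patient going from (16, 1, 1.0) to (10, 1, 1.0) by day 7 still resumes.
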